2.1.7 Statistical Considerations and Sample Size

Power and Sample Size: The total enrollment proposed for this study is of 800 subjects: 600 Blacks and 200 Hispanics. Amongst them, we expect approximately 80-160 ATTR CA subjects and 640-720 non-amyloid controls. The sample size planned for each race/ethnicity group achieves 80% power to

detect, as in Aim 1: (1) a prevalence of ATTR-CA of 10-15%, (2) a two-fold difference in the prevalence of ATTRm between Blacks and Hispanics (i.e., 0.08 vs 0.04, respectively), as well as, a similar difference in the prevalence of ATTRwt between Blacks and Hispanics, (3) a difference as small as 0.03 (if one truly exists) in the prevalence of ATTRwt with respect to gender (male) distribution between the two race/ethnic groups, and (4) in the ATTR CA group alone, we plan to measure the hierarchical composite endpoint of death, heart failure hospitalization, and 30% decline in 6-minute hall walk after 1 year. A two-sided logrank test with an overall sample size of 80 subjects (40 in the ATTRwt and 40 in the ATTRm) achieves 82% power at a 0.05 significance level to detect a hazard ratio (HR) of 0.44 when the proportion of patients that did not progress in the mutant group is 0.60. This corresponds to a minimum difference of 15% in the probability of not having progressed past 12 months between the two groups.

Aim 2 focuses on comparing differences in TTR kinetic stability and RBP4 concentration between ATTR CA (N=80-120) and the non-amyloid group (N=680-720). These sample sizes generate >95% power to detect: Hypothesis 1) a minimum difference in RBP4 of 5, assuming SDs of 9 and 20 for ATTR CA and non-amyloid, respectively; Hypothesis 2) a mean change difference in TTR stability as small as 0.01, SD of 0.002.

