2.1.1 Research Goal

The goal of our research is to change the approach to transthyretin cardiac amyloidosis, which is a devastating disease, by screening and early diagnosis, and by studying prospectively a cohort of older Blacks/Hispanics with heart failure in order to address the following aims and hypotheses:

Specific Aim 1: To determine the prevalence of ATTR CA in Caribbean Hispanics and Blacks with HF. The hypotheses to be tested include:

- (1) the prevalence of ATTR CA will be 10-15%
- (2) ATTRwt CA will be higher among Caribbean Hispanics compared to US Blacks, whereas the prevalence of ATTRm CA will be lower
- (3) the gender distribution of ATTR CA identified by this active ascertainment approach will be similar
- (4) disease progression will demonstrate that ATTRm is associated with a more rapid decline vs. ATTRwt
- (5) the accuracy of our clinic-based risk calculator will be confirmed in this large prospectively recruited cohort

Specific Aim 2: To demonstrate that circulating RBP4 concentration is integral to TTR tetramer stability which in turn determines the clinical characteristics of ATTR CA. We will measure TTR tetramer stability and RBP4 concentration in serum and urine collected in Aim 1. The hypotheses to be tested include:

- (1) TTR tetramer stability will be lower in ATTR CA and directly relate to RBP concentration
- (2) TTR tetramer stability will associate with clinical features and
- (3) Increased renal clearance of RBP4 in ATTR CA will be determined by measurement of RBP4 in plasma and urine.

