2.1.8 Data Analysis Plan

Descriptive statistics will be used to summarize subjects' demographics and study outcomes. Sample proportions with exact 95% confidence intervals will be used to estimate the overall prevalence of ATTRm CA in Blacks and Hispanics and by sex. All analyses will be performed in SAS v.9.4 (Cary,NC), at a significance level of 0.05.

AIM 1: Hypotheses 1-3: The differences in proportions for prevalence (#1), genetic mutation status (#2), and sex (#3) will be assessed using Chi-squared/Fisher Exact tests. The genetic ancestry analysis will use 500K SNP data to perform principal components analysis (PCA) and determine the percentage of African admixture in all participants. To identify the associations of rare genetic variants in the TTR gene in ATTR CA cases vs controls, we will utilize burden testing.⁹⁴ **Hypothesis 4:** The main analysis will use the Kaplan-Meier method to estimate the probabilities of the composite endpoint, with medians (95% CI) being reported for each group. Cox regression analysis will be performed to generate the hazard ratio (95% CI), and to allow adjustment for other covariates such as sex or race/ethnicity, or explore interaction with other variables including cardiac biomarkers, echo parameters, or QOL. Alternatively, we will apply and compare Finkelstein-Schoenfeld's unmatched approach⁹⁵ to the matched win ratio,⁹⁶ both methods being used for reporting composite endpoints, with more appropriate priority given to the more clinically important event, e.g. mortality. **Hypothesis 5:** We will test the clinic-based risk calculator that was previously developed and validated in a smaller matched cohort study.⁹⁷ The proposed 4-variable model included: RBP4, LVEF, inter-ventricular septal thickness, mean limb lead QRS voltage, and generated an ROC AUC >90%. This model will be tested in our larger cohort and assessed with respect to prediction capability (AUC ROC) and goodness-of fit (Hosmer-Lemeshow test). We also plan to fit additional multivariable logistic regressions using the variables collected employing variable selection/model-building strategies and comparing the

resulting model(s) to the one proposed above. The variables in the final clinical risk model will be based on weights from the multivariate model.

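### The stated 80% power for ATTRm prevalence of 0.08 versus 0.04 is about 48% with 600 Black and 200 Hispanic participants

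*Combined protocol and SAP*

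**What the plan says.** Section 2.1.7 (Statistical Considerations and Sample Size) sets total enrolment at 800, made up of "600 Blacks and 200 Hispanics"; Table 3 in section 2.1.3 gives the same totals. It then says: "The sample size planned for each race/ethnicity group achieves 80% power to" detect four things under Aim 1. Item (2) is "a two-fold difference in the prevalence of ATTRm between Blacks and Hispanics (i.e., 0.08 vs 0.04, respectively"), together with "a similar difference in the prevalence of ATTRwt between Blacks and Hispanics". Item (1) is an overall ATTR-CA prevalence of 10-15%. Item (3) is "a difference as small as 0.03 (if one truly exists) in the prevalence of ATTRwt", in relation to the proportion of men in the two groups.

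Section 2.1.8 (Data Analysis Plan) says that differences in prevalence, mutation status and sex "will be assessed using Chi-squared/Fisher Exact tests" at a 0.05 significance level. For estimation, "exact 95% confidence intervals will be used to estimate the overall prevalence of ATTRm CA in Blacks and Hispanics and by sex".

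Section 2.1.1 (Research Goal) includes among the hypotheses to be tested under Specific Aim 1 that "ATTRwt CA will be higher among Caribbean Hispanics compared to US Blacks, whereas the prevalence of ATTRm CA will be lower".

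**The concern.** Item (2) gives everything needed to check its power: two group sizes, two rates, a family of tests and a level. With 200 people in the smaller group and a rate of 4%, only 8 Hispanic cases are expected, which is few for separating 4% from 8% with 80% power.

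If the true power is near one half, the planned test is about as likely to miss the sponsor's own two-fold difference as to find it. A reader who trusts 80% could take a non-significant result as fair evidence that ATTRm prevalence is similar in the two groups. The intervals planned in section 2.1.8 would not prevent this, because they describe prevalence within groups and not the difference between them.

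The neighbouring items carry the same 80% but omit inputs, so a reader cannot tell whether they are sound.

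**Working it through.** **Inputs.** n₁ = 600 Black and n₂ = 200 Hispanic participants (2.1.7, Table 3); p₁ = 0.08, p₂ = 0.04 (2.1.7); chi-squared or Fisher exact test, level 0.05 (2.1.8). Sidedness is not stated for this item. I take it as two-sided, because that is how the chi-squared test works and because the logrank test in the same section is two-sided; one-sided results are also given. No allowance is made for dropout, since section 2.2 expects none before the blood sample.

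**Attempt to reproduce 80%.** The normal formula that matches the chi-squared test is

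power = Φ[(|p₁ − p₂| − z·SE₀) / SE₁]

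- Pooled rate: (600×0.08 + 200×0.04)/800 = 56/800 = 0.07
- SE₀ = √[0.07×0.93×(1/600 + 1/200)] = 0.02083
- SE₁ = √[0.08×0.92/600 + 0.04×0.96/200] = 0.01774
- (0.04 − 1.96×0.02083)/0.01774 = −0.047, and Φ(−0.047) = 0.481

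Power is 48.1%, not 80%.

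**Other two-group conventions at 600/200.**

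| Method | Two-sided | One-sided |
|---|---|---|
| Pooled normal | 48.1% | 62.7% |
| Unpooled normal | 61.6% | 72.9% |
| Arcsine | 55.2% | 67.3% |
| Continuity-corrected | 40.7% | 55.4% |
| Exact enumeration, Pearson | 49.8% | 64.8% |
| Exact enumeration, Fisher | 48.2% | 59.1% |

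Exact enumeration of the two-sided likelihood-ratio test gives 54.0%. None reaches 80%.

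**The result at exactly the hypothesised rates.** The table is 48/600 versus 8/200. The chi-squared statistic is (0.04/0.02083)² = 3.69, p = 0.0549; Fisher p = 0.0558. The Newcombe 95% interval for the difference is −0.2 to 7.1 percentage points. This restates the power result rather than adding to it: power near 50% means that the assumed effect sits near the critical value.

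**What 80% would take (two-sided, pooled).**

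- At 3:1: about 1,166 + 389 = 1,555 participants.
- At 1:1: 553 per group.
- With 600 Black participants: about 520 Hispanic participants.
- Within 800, the best split (about 360/440) gives 67%.
- At 600/200 with 8% in Black participants, the Hispanic rate must fall to about 2.7% (0.0267 pooled, 0.0276 exact chi-squared, 0.0270 Fisher), a ratio of 0.08/0.027, or about three-fold.

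**The companion claims.** These cannot be reproduced, because inputs are missing.

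- ATTRwt difference: no rates are given. Section 1.1.2 says that ATTRwt prevalence in African-Americans is unknown, and section 2.1.6 offers only 2-8% for Hispanics. On assumed Black/Hispanic rates (pooled, two-sided, 600/200), a two-fold contrast has about 23% power at 0.01/0.02, 37% at 0.02/0.04 and 60% at 0.04/0.08. Read instead as an absolute difference of 0.04, power is 60% at 0.04/0.08, 76% at 0.02/0.06 and 87% at 0.01/0.05.
- The 0.03 gender item: no base rate or denominator is given. With an assumed lower rate of 0.5% to 5%, power runs from 14% to 60% for 300 versus 100 men, and from 27% to 82% for the whole groups, depending also on which group is higher.
- Prevalence of 10-15%: no null or comparator value is named, so power is undefined. The exact 95% intervals at n=800 would be 8.0% to 12.3% for 80/800 and 12.6% to 17.7% for 120/800.

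**The case against.** The strongest reply is that Aim 1 is mainly about estimating prevalence. The synopsis places the Black-Hispanic comparison among matters to explore, and Hypothesis 2 in section 2.1.6 uses similar language. On that view this is one wrong figure in a supporting sentence. The context is fair, but section 2.1.1 also lists the contrast among hypotheses to be tested, section 2.1.8 gives it a test, and section 2.1.7 attaches an explicit 80% to it. Exploratory status does not make the figure right.

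A second reply is that the reference to each race/ethnicity group could mean one-sample calculations. Some of these do exceed 80%: 600 Black participants at 0.08 against a fixed 0.04 gives 98.6%, and 200 people at 0.08 against a fixed 0.04, one-sided, gives about 81.5%. Neither is a difference between the two groups, and the second gives the smaller group the rate assigned to the larger. Hispanic participants at 0.04 against a fixed 0.08 reach only 56.9% two-sided and 72.9% one-sided. The statement that nothing reaches 80% should therefore be confined to two-group tests.

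Third, two tests would be significant at exactly the assumed rates: Wald (p=0.024) and likelihood-ratio (p=0.042). Neither is the planned test, and their two-sided power is still only 61.8% and 54.0%.

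Finally, the ATTRwt and 0.03 ranges depend on rates chosen for illustration. That stands. They show that the answer depends on unstated inputs, not that the claims are false.

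**Conclusion.** The 80% figure for ATTRm 0.08 versus 0.04 is wrong on the plan's own inputs. Power is about 48% for the planned tests, two-sided at 0.05, with 600 and 200 participants. The two-sided reading is an inference, but the conclusion does not depend on it, since one-sided testing gives 55% to 73%. The shortfall is not a matter of allocation either, as no split of 800 takes the two-sided pooled test above 67%.

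The ATTRwt and 0.03 claims are unverifiable rather than shown to be wrong, and the 10-15% item is incomplete as a power statement. These are secondary. The ATTRm figure must be corrected because readers would use it to interpret a non-significant comparison.

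**What to change.** Keep N=800.

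- In 2.1.7 item (2), give the ATTRm power as about 48% for 0.08 versus 0.04, or say that 80% is reached only for about a three-fold contrast (8% versus about 2.7%). State the test and its sidedness.
- For the ATTRwt contrast and the 0.03 gender item, the sponsor should state the assumed rates and denominator and recompute at 600/200, or remove the claims.
- Replace the power claim for a prevalence of 10-15% with the expected exact 95% intervals at n=800 given above.
- In 2.1.8, add that Black-Hispanic differences in prevalence will be reported with 95% confidence intervals alongside the tests. This is a reporting improvement that lets a non-significant result be read properly.

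The cost is some rewording in 2.1.7, one sentence in 2.1.8 and a less favourable stated power. No participants or procedures are added.

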2.1.6 Hypotheses

Aim 1: To determine the prevalence of ATTR CA in Caribbean Hispanics and Blacks with HF

Hypothesis 1. Overall prevalence of ATTR CA: The prevalence of ATTR CA will be defined by the number of cases with both ATTRwt and ATTRm CA as a percentage of total enrollment. The background prevalence of Val122Ile in the US Black population is 3.4%, and we hypothesize a prevalence rate of 8% of ATTRm Val122Ile in our outpatient HF population. Since there are no data in Hispanics regarding ATTR CA prevalence, we further hypothesize that we will observe a prevalence of ATTRwt CA of 2-8% of the Hispanic population. Thus, we have conservatively defined the predicted prevalence of ATTR CA as 10-15%.

Hypothesis 2. Relative proportion of ATTR CA comprised by ATTRwt and ATTRm: As noted above, based upon the background allele frequency, we anticipate that Black patients will be much more likely to manifest ATTRm (Val122Ile) vs. ATTRwt CA, whereas Hispanic patients will be more likely to manifest ATTRwt CA. We will be able to explore the Val122Ile genotype frequency in the Hispanic population, and with the addition of cardiac amyloid scintigraphy scanning, the relative contribution of ATTRm in this population, which we postulate to be lower than Blacks. We will utilize genetic ancestry analysis data to further characterize race and ethnicity, and, as an exploratory analysis, evaluate the interaction of genetic variants identified with Val122Ile and ATTR CA as defined by radiotracer uptake.

Hypothesis 3. Proportion of gender: Published reports of ATTR Val122Ile are 75% male and reports of ATTRwt are 95% male. We hypothesize that highly sensitive cardiac amyloid scintigraphy testing will reveal a gender distribution of ATTR that is closer to 50%, based upon allele distribution. We will explore comorbidities, TTR stability, and RBP4 differences among men and women with ATTR to determine interactions with phenotypic expression.

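### The 80% power claimed for a Black–Hispanic difference in ATTRwt prevalence has no stated rates behind it; read as a two-fold difference, two-sided power is about 23% to 60%

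*Combined protocol and SAP*

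**What the plan says.** Section 2.1.7 sets enrolment at "800 subjects: 600 Blacks and 200 Hispanics" and states: "The sample size planned for each race/ethnicity group achieves 80% power to" detect several listed effects. Item (2) of that list is a two-fold ATTRm difference, with 0.08 in Blacks and 0.04 in Hispanics, followed by "as well as, a similar difference in the prevalence of ATTRwt between Blacks and Hispanics". The second clause carries no prevalence figures.

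The rest of the plan supplies part of what is missing:

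- **Direction.** Section 2.1.1, Specific Aim 1, hypothesis (2): "ATTRwt CA will be higher among Caribbean Hispanics compared to US Blacks".
- **Hispanic rate.** Section 2.1.6, Aim 1, Hypothesis 1: "we will observe a prevalence of ATTRwt CA of 2-8% of the Hispanic population".
- **Test and level.** Section 2.1.8: the Aim 1 differences in proportions "will be assessed using Chi-squared/Fisher Exact tests", with all analyses "at a significance level of 0.05".
- **Black rate.** No numerical ATTRwt prevalence in Black heart failure patients is given as a planning assumption.
- **Sidedness.** Not stated for the proportion tests. The only mention in section 2.1.7 belongs to another analysis: "A two-sided logrank test with an overall sample size of 80 subjects".

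**The concern.** The ATTRwt clause borrows its power figure from the ATTRm clause, but the two contrasts differ in ways that matter. For ATTRm the higher rate sits in the group of 600; for ATTRwt it is predicted in the group of 200. The base rate also differs, since Hispanic ATTRwt may be as low as 2%. Rare outcomes and a 3:1 split both reduce power, so 80% cannot simply be carried over.

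The ATTRwt prediction is one half of Aim 1 hypothesis (2), and section 2.1.6 says there are no data on ATTR-CA prevalence in Hispanics. A reader who trusts 80% could take a non-significant result as a sign that the groups have similar ATTRwt prevalence. Section 2.1.8 promises exact confidence intervals for ATTRm prevalence only, so no planned interval would show how imprecise the ATTRwt comparison is.

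**Working it through.** **Inputs.** n_B = 600 and n_H = 200 (2.1.7); alpha 0.05 (2.1.8), taken as two-sided first; Hispanic rate p_H from 2% to 8% (2.1.6); Hispanics higher (2.1.1). *Similar* is read first as two-fold, so p_B = p_H/2, or 1% to 4%. That Black rate is an assumption.

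**The plan's own figure.** The 80% cannot be reproduced directly, because no ATTRwt rates are given. Copying the ATTRm rates (Black 8%, Hispanic 4%) gives 48% two-sided and reverses the predicted ATTRwt direction.

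**Formula (pooled chi-square, normal approximation).**

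- p̄ = (600·p_B + 200·p_H)/800
- SE0 = √[p̄(1−p̄)(1/600 + 1/200)]
- SE1 = √[p_B(1−p_B)/600 + p_H(1−p_H)/200]
- Power = Φ[(p_H − p_B − z·SE0)/SE1], with z = 1.96 two-sided or 1.645 one-sided

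**Worked case, Hispanic 8% v Black 4%.** p̄ = 0.05, SE0 = 0.0178, SE1 = 0.0208. Power = Φ[(0.04 − 1.96 × 0.0178)/0.0208] = 0.597. One-sided, the same formula with 1.645 gives 0.697.

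**Two-fold difference across the plan's range.**

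| Hispanic v Black | SE0 | SE1 | Two-sided | One-sided |
|---|---|---|---|---|
| 8% v 4% | 0.0178 | 0.0208 | 59.7% | 69.7% |
| 6% v 3% | 0.0155 | 0.0182 | 49.1% | 59.7% |
| 4% v 2% | 0.0127 | 0.0150 | 37.0% | 47.4% |
| 2% v 1% | 0.0091 | 0.0107 | 23.4% | 32.3% |

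**Choice of method.** At 8% v 4%, two-sided, full binomial enumeration gives 59.5% for the uncorrected chi-square and 54.8% for Fisher's exact test. Arcsine gives 55.2% and unpooled variance 48.6%. Enumerated one-sided chi-square power is 70.1%. At 2% v 1%, enumeration gives 23.3% (chi-square) and 18.7% (Fisher).

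**What 80% would take.** At 600 v 200, two-sided, the Black rate would have to be about 3.0% if Hispanics are at 8% (8/3.04 = 2.6-fold), 1.8% at 6% (6/1.84 = 3.3-fold) and 0.8% at 4% (4/0.79 = 5.1-fold). Keeping the ratio at two and the split at 3:1, 8% v 4% needs 343 Hispanics and 1,029 Blacks (1,372 in all), and 2% v 1% needs 1,435 and 4,305 (5,740 in all).

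**Absolute reading: a 4-point gap, Hispanics within 2–8%.**

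| Hispanic v Black | Ratio | Two-sided | One-sided |
|---|---|---|---|
| 8% v 4% | 2.0 | 59.7% | 69.7% |
| 7% v 3% | 2.3 | 67.2% | 76.0% |
| 6% v 2% | 3.0 | 76.3% | 83.2% |
| 5.5% v 1.5% | 3.7 | 81.3% | 87.0% |
| 5% v 1% | 5.0 | 86.5% | 90.8% |

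**The case against.** The strongest reply is that the plan leaves the ATTRwt effect undefined, so the 80% cannot be called a failed calculation. The word *similar* follows a pair of rates 0.04 apart, and an absolute gap of that size does reach 80% within the 2–8% range once the Black rate is low enough. Sidedness is open as well, and the prediction is directional. These points stand in part. Because of them, a reader who inferred that power is at most 60% in every case, or that 80% is out of reach on any reading, would be going further than the documents allow. The 60% ceiling is for two-sided testing of a two-fold difference, and every Black rate used here is inferred.

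The reply still does not rescue the clause. The sentence describes its effect as two-fold, which is the plain referent of *similar*. Where the absolute reading passes 80%, the ratio is about three-fold or more at the points computed (6% v 2% one-sided, 5.5% v 1.5% two-sided). At 7% v 3%, one-sided power is still only 76%.

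It can also be said that the comparison is secondary. The Synopsis lists the Hispanic–Black comparison as exploratory and names only the Val122Ile genotype and ATTRm phenotype, and section 2.1.8 labels the second test as mutation status. That limits the importance of the point, but section 2.1.1 does state the ATTRwt hypothesis and section 2.1.7 does attach a power figure to it. No passage says that a null result will be read as equivalence; that is a risk for readers, not a stated intention.

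**Conclusion.** The ATTRwt power claim is unsupported as written. With 600 v 200, alpha 0.05 and Hispanics higher, no two-fold difference with Hispanic ATTRwt between 2% and 8% gives 80% power. At the top of the range the two-sided shortfall is about 20 points (80 − 60), and a true doubling would be missed about 40% of the time. At the bottom it would be missed about 77% of the time.

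This rests on two assumptions: that *similar* means two-fold, and that the Black rate is therefore half the Hispanic rate. The conclusion survives a change of test method or of sidedness. It changes only if *similar* means a 4-point absolute gap and the Black rate is about 1.5% or lower (two-sided) or about 2% (one-sided), and the plan states neither condition. The calculation makes no allowance for unreadable scans or withdrawals, which would lower power further. The point does not reach the overall prevalence estimate or the other power claims in section 2.1.7.

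**What to change.** **Section 2.1.7, item (2).** Replace the ATTRwt clause with its own statement giving the assumed ATTRwt rate in each group, the direction (Hispanics higher), the sidedness and the recomputed power. The sponsor should supply the Black rate. If the two-fold assumption is kept, the text could read: *With 600 Blacks and 200 Hispanics, two-sided power for a two-fold higher ATTRwt prevalence in Hispanics is about 60% for 8% v 4%, 37% for 4% v 2% and 23% for 2% v 1%.* If an absolute gap was meant, say so and give the rates at which 80% holds. Correct the ATTRm clause in the same edit: its stated rates of 8% v 4% give 48% two-sided by the same formula.

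**Section 2.1.8.** Add the Hispanic–Black difference and ratio in ATTRwt prevalence, each with a 95% confidence interval, and state that a non-significant test is not evidence of equal prevalence.

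**Cost.** Wording only, with no extra patients or procedures. The one downside is a less favourable stated power.

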2.1.3 Patient Recruitment

The SCAN- MP study is designed to identify a sufficient number of cases to support the following analytical objectives:

1. Stratify prevalence of ATTR-CA in subjects with HF by relevant demographic characteristics (gender, race/ethnicity, genotype); and
2. Evaluate relationships among ATTR-CA and baseline risk factors (presence of Val122Ile mutation and others) with disease outcomes.

To accomplish these objectives, a hybrid approach to cohort identification and selection is used that combines deliberate selection of subjects with heart failure who are at increased risk for ATTR-CA and selection of participants with relevant characteristics (age, gender, race/ethnicity, country of origin). Planned proportion of enrolled subjects by relevant characteristics is shown in the Table 3. Community involvement is essential for its success and recruitment will involve intensive community engagement through various means among the sites. In aggregate, we will recruit an equal number of men and women from the racial/ethnic groups. The expected marginal distributions of race/ethnicity are shown in Table 3. We will have overlapping ethnic groups among centers to minimize confounding of ethnicity by site. As recruitment of elderly members of minority groups is challenging, toward end of the recruitment period, participants will be asked to refer elderly persons to the study.

Table 3. Planned Enrollment by Age, Race, and Gender

Age (yr)	Black		Hispanic or Latino ethnicity		Total	
	M	F	M	F	M	F
≤75	150	150	50	50	200	200
>75	150	150	50	50	200	200

At CUMC we have seen 24,682 unique patients with HF over the last five years of which 2,969 (12%) self-identified as Black and 4,387 of 14,466 (29.9%) patients who declared their ethnicity were Hispanic and whose average age was 63 years. Harlem Hospital provides health care services to the primary service area of Harlem, Washington Heights/Inwood and the South Bronx with the vast

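### The 80% power claimed for a 0.03 difference in ATTRwt prevalence among men of the two race/ethnic groups comes with no baseline, and is about 14-38% for 300 v 100 men when the lower prevalence is 2-5%

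*Combined protocol and SAP*

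**What the plan says.** Section 2.1.7 opens with the enrolment: "The total enrollment proposed for this study is of 800 subjects: 600 Blacks and 200 Hispanics". It continues: "The sample size planned for each race/ethnicity group achieves 80% power to" detect a numbered list of effects. Item (3), which compares Blacks with Hispanics, is "a difference as small as 0.03 (if one truly exists) in the prevalence of ATTRwt with respect to gender (male) distribution". Unlike item (4), which has its own group sizes, test and power, item (3) is given no prevalence in either group, no subgroup size and no sidedness.

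The other inputs are elsewhere in the protocol:

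- Section 2.1.3 says "In aggregate, we will recruit an equal number of men and women from the racial/ethnic groups". Table 3 there ("Planned Enrollment by Age, Race, and Gender") plans 300 Black men, 300 Black women, 100 Hispanic men and 100 Hispanic women.
- Section 2.1.6 hypothesises "a prevalence of ATTRwt CA of 2-8% of the Hispanic population". It gives no ATTRwt prevalence for Blacks and none by sex.
- Section 2.1.8 says that the differences for Hypotheses 1-3 "will be assessed using Chi-squared/Fisher Exact tests", and "All analyses will be performed in SAS v.9.4 (Cary,NC), at a significance level of 0.05".
- Section 2.1.1 expects ATTRwt to be more common in Caribbean Hispanics than in US Blacks.

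**The concern.** Three percentage points is a small gap to detect when the smaller group is 100 men. At 2% v 5%, for example, the expected counts are 6 cases among 300 Black men and 5 among 100 Hispanic men. Counts of that size cannot normally carry 80% power.

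The stated figure matters because sex distribution is a named Aim 1 hypothesis, and section 2.1.1 predicts that it will be similar in men and women. A non-significant result would agree with that prediction, and an 80% power statement would give it weight. If true power is 14-38%, a real 3-point difference among men would be missed 62-86% of the time.

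**Working it through.** **The plan's figure.** It cannot be rebuilt from the text, because item (3) gives no baseline. The check is therefore to find which baselines, if any, return 80%.

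**Inputs.** Gap 0.03 and claimed power 80% (2.1.7); 300 Black and 100 Hispanic men, 400 men and 400 women (Table 3); 600 and 200 overall (2.1.7); chi-squared or Fisher test at 0.05 (2.1.8). Two-sided testing is assumed. A lower prevalence of 2-5% keeps both groups inside 2-8%; using that range for Blacks, and for men alone, is an assumption.

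**Formula (normal approximation).** Power = Φ((|p₁ − p₂| − 1.96·s₀)/s₁), where s₀ = √[p̄(1−p̄)(1/n₁+1/n₂)], s₁ = √[p₁(1−p₁)/n₁ + p₂(1−p₂)/n₂] and p̄ is the pooled prevalence.

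**Worked case: 300 Black men at 2%, 100 Hispanic men at 5%.**
- p̄ = (6 + 5)/400 = 0.0275
- s₀ = √(0.0275 × 0.9725 × 0.01333) = 0.01888
- s₁ = √(0.02 × 0.98/300 + 0.05 × 0.95/100) = 0.02325
- Power = Φ((0.03 − 0.03701)/0.02325) = Φ(−0.301) = 0.38

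Summing the two binomial distributions over every outcome at which the uncorrected chi-squared test rejects gives 0.383.

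**All readings, by that full enumeration:**

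| Prevalences | Men 300 v 100, Hispanics higher | Men 300 v 100, Blacks higher | All 600 v 200, Hispanics higher | All 600 v 200, Blacks higher | 400 men v 400 women |
|---|---|---|---|---|---|
| 2% v 5% | 0.383 | 0.185 | 0.576 | 0.452 | 0.649 |
| 3% v 6% | 0.301 | 0.161 | 0.475 | 0.367 | 0.535 |
| 4% v 7% | 0.243 | 0.148 | 0.412 | 0.315 | 0.459 |
| 5% v 8% | 0.209 | 0.139 | 0.358 | 0.279 | 0.406 |
| 1% v 4% | 0.513 | 0.220 | 0.750 | 0.596 | 0.807 |
| 0.5% v 3.5% | 0.613 | 0.224 | 0.871 | 0.720 | 0.900 |
| near 0 v 3% | about 0.80 | about 0.19 | over 0.9 | over 0.9 | over 0.9 |

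Fisher's test lowers the range for men at a 2-5% base to 13-32%. With both prevalences inside 2-8%, no two-group reading reaches 80% even one-sided; the highest value is 76% (400 v 400, arcsine approximation, 2% v 5%).

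**Difference with 80% power** (the formula above solved for the gap, lower prevalence 2% to 5%):
- 300 v 100 men: 0.067 to 0.090 with Hispanics higher; 0.080 to 0.100 with Blacks higher.
- 600 v 200: 0.043 to 0.059 with Hispanics higher; 0.049 to 0.065 with Blacks higher.

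**Size needed for 0.03.** At 3:1 with Hispanics higher, 80% power needs about 356 Hispanic and 1,068 Black men (5% v 2%), rising to 674 and 2,022 (8% v 5%).

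**The case against.** The best defence is that the plan never gives 2% as a floor for Blacks. The 2-8% is stated for Hispanics, ATTRwt is expected to be less common in Blacks, and section 2.1.6 expects Black patients to have mostly the Val122Ile form. A Black rate of 0.5% against a Hispanic rate of 3.5% fits the text and gives 87% power at 600 v 200. Section 2.1.6 also says that published ATTRwt cases are 95% male. With equal numbers of each sex, a 95% share means a male rate 19 times the female rate. A 0.03 gap is then 18 times the female rate, so about 0.17% in women and 3.17% in men, and 400 v 400 has about 97% power.

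This stands as far as it goes. A reader might infer that the 80% claim fails under every reading. The documents do not support that: several contrasts exceed 80% when the lower prevalence is very low.

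It does not rescue item (3) as written. The item describes a contrast between race/ethnic groups with respect to men, which a men-v-women comparison is not, and Hypothesis 3 itself predicts a split closer to 50%. For 300 v 100 men, 80% is reached only with a Black rate near zero, and the plan states no such rate. With Blacks higher, the lower rate belongs to Hispanics, for whom the plan's own floor is 2%. A one-sample test can exceed 80% (87% for n = 300, 2% v 5%), but that does not compare two groups.

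A reader might also infer that the study will present a null result as proof of no sex difference. No passage says so. The synopsis lists sex differences as exploratory, and section 2.1.8 already plans exact intervals by sex, though for ATTRm.

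**Conclusion.** Item (3) is wrong as written: it states 80% power for an unspecified contrast, and on the literal reading the design does not have it. For 300 Black v 100 Hispanic men and a two-sided chi-squared test at 0.05, power for a 0.03 gap is about 21-38% with Hispanics higher and 14-19% with Blacks higher, at a lower prevalence of 2-5%. The first range rests on extending the Hispanic 2-8% to Blacks; both rest on applying it to men. Relaxing the assumption about Blacks to 1% v 4% gives about 51%.

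The wider readings fall short at a 2-5% base (28-58% for 600 v 200, 41-65% for 400 v 400) and reach 80% only with a lower prevalence of about 1% or less. If the authors assumed such a rate, the protocol does not say so. The conclusion is limited to this power statement and does not call the prevalence estimates into question.

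**What to change.** Rewrite item (3) of section 2.1.7 to name the contrast and its group sizes, the assumed ATTRwt prevalence in each group, and the sidedness. Then replace the 80% claim with one of these:

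- the actual power for 0.03, about 14-38% for 300 v 100 men at a 2-5% base; or
- the difference that has 80% power at that base: about 0.07-0.09 for men with Hispanics higher, 0.08-0.10 with Blacks higher, or about 0.043-0.065 if 600 v 200 is meant.

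If a Black rate near zero was the planning assumption, state it and give its basis. In section 2.1.8, add that the ATTRwt difference will be reported with a 95% confidence interval, so that a non-significant test is read with its precision.

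The cost is a change of wording and a less favourable stated figure. No extra patients or procedures are needed.
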